4.2 Missing Data Conventions

Partial and missing AE and concomitant medication dates will be imputed with maximum conservatism. If the onset date is missing or partial, the date will be compared as far as possible with the date of first dose of study medication. If no month is present and it is in the same year as the date of first treatment, or the year and month are the same as the first treatment date, the onset date will be imputed as the date of first treatment. Otherwise it will be imputed as 01 January in the available year, or the first day of the month and year available. End dates will be imputed as 31 December in the available year, or the last day of the available month and year collected. Partial dates will be presented in listings, along with classifications of TEAE for AEs or Prior/Concomitant/Both for medications.

Missing data will generally be left as missing, except for partial and missing AE and concomitant medication dates. Special cases, e.g. below the limit of quantification, will be described in the sections that describe the specific parameter's analysis.

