9.1 Main Efficacy Analysis

9.1.1 Patient Diary - Influenza Patient Reported Outcomes (FluPRO)

The FluPRO is a 32 question instrument that assesses occurrence and severity of influenza symptoms over the last 24 hours. The instrument questions, and the conversion from text to numeric values, are presented in Sec. 17.3.

The FluPRO data is collected at Day 1: Baseline, then every day through Day 10. These data will be summarized at each visit with counts and percentages by treatment group, including a combined low-dose and high-dose VIS410 group. This analysis will be performed using the mITT population.

The domain, component, and total symptom scores for an individual will be calculated as the mean of the questions that are non-missing. The minimum data requirement for calculating each of the domain symptom scores is: nose 3 of 4 items, throat 2 of 3 items, eyes 2 of 3 items, chest/respiratory 5 of 7 items, gastrointestinal 3 of 4 items, and body/systemic 8 of 11 items. Total symptom scores will only be calculated if the conditions of missing data for all domains are met.

The domain symptom scores are defined as:

- Nose: Running or dripping nose, congested or stuffy nose, sneezing, sinus pressure
- Throat: Scratchy or itchy throat, sore or painful throat, difficulty swallowing
- Eyes: Teary or watery eyes, sore or pain eyes, eyes sensitive to light
- Chest/Respiratory: Trouble breathing, chest congestion, chest tightness, dry or hacking cough, wet or loose cough, coughing, coughed up mucus or phlegm
- Gastrointestinal: Nausea, stomach ache, vomiting, diarrhea
- Body/Systemic: Felt dizzy, head congestion, headache, lack of appetite, sleeping more than usual, body aches or pains, weak or tired, chills or shivering, felt cold, felt hot, sweating

The component symptom scores are defined as:

- Upper Respiratory Tract: Runny or dripping nose, congested or stuffy nose, scratchy or itchy throat, sore or painful throat, sneezing, difficulty swallowing, teary or watery eyes, sore or painful eyes, eyes sensitive to light,
- Lower Respiratory Tract: Trouble breathing, chest congestion, chest tightness, coughing, dry or hacking cough, wet or loose cough, coughed up mucus or phlegm
- Generalized: Nausea, vomiting, diarrhea, stomach ache, felt dizzy, sinus pressure, head congestion, headache, lack of appetite, sleeping more than usual, body aches or pains, weak or tired, chills or shivering, felt cold, felt hot, sweating

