Time to resolution (in days) for the total symptom score, each domain symptom score (nose, throat, eyes, chest/respiratory, gastrointestinal, body/systemic) and each component symptom score (upper respiratory tract, lower respiratory tract, and generalized) will be summarized using n, mean, SD, median, minimum, and maximum. Kaplan-Meier methods will also be used to calculate the median time, 25th percentile, and 75th percentile time to resolution. These summaries will be by treatment group and include the combined low-dose and high-dose VIS410 groups in the mITT population. For individual symptom questions 1 to 32, a value of 0 or 1 corresponds to resolution of that symptom. Time to resolution of the total symptom, domain symptom scores and component symptom scores will be defined as the maximum time to resolution for the individual questions that comprise that total, domain or component symptom score.

The duration of an individual symptom will be defined as the earliest visit day from 2 consecutive answers of ‘no symptom’ defined as ‘Not at all’ or ‘A little bit’ for questions 1 – 27; ‘Never’ or ‘Rarely’ for questions 28 - 30 and ‘0 times’ or ‘1 time’ for questions 31 and 32. The duration of total symptom score, domain symptom scores, or component symptom scores will be primarily defined as the earliest visit day from 2 consecutive means ≤ 1.0 ; and as an exploratory endpoint as the maximum value of duration across the individual symptoms questions that comprise that total, domain or component symptom score. A missing value cannot contribute to the 2 consecutive ‘no symptom’ days. If a subject has ‘no symptoms’ at Baseline for a question, total symptom score, domain symptom scores, and component symptom scores, duration will be defined as zero for that question. If a subject has not had 2 consecutive ‘no symptom’ responses or 2 consecutive means ≤ 1.0 by the Day 10 FluPRO survey, the subject’s data will be listed as “>10” and summarized as 10 days. Kaplan-Meier methods will also be used to calculate the median time, 25th percentile, and 75th percentile time to resolution.

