The total symptom score, the 6 domain symptom scores, and the 3 component symptom scores will be summarized by treatment group at each visit (including change from baseline and percent change from Baseline to each visit), including the combined low-dose and high-dose VIS410 group with n, mean, SD, median, minimum, and maximum by treatment group, including a combined low-dose and high-dose VIS410 group.

The count and percentage of subjects with a mean score ≤ 1.0 for the total symptom score, 6 domain symptom scores, and 3 component score will be summarized at each post-baseline visit. An additional summary of counts and percentages of subjects with a score of 0 or 1 for all of the individual symptom scores composing the total symptom score, 6 domain symptom scores, and 3 component symptom scores will also be presented for each post-baseline visit. These summaries will also be presented by region: USA, South Africa, and the rest of the world.

Area under the curve (AUC) for the total symptom score, 6 domain symptom scores, and 3 component symptom scores will be calculated using the linear trapezoidal rule, i.e. $AUC_{t_i, t_{i+1}} = 1/2 * (S_i + S_{i+1}) * (t_{i+1} - t_i)$ where S_i is the total symptom score at time point t_i . All time points from pre-dose to Day 10 will be considered.

A sensitivity analysis of the total symptom score, domain symptom scores, and component symptom scores will be conducted by repeating the above analysis in the mITT population,

excluding subjects who received antiviral therapy for influenza during the first 10 days of the study. Determination of applicable antiviral therapy for influenza will be defined before the study is unblinded.

Additional exploratory analysis, including but not limited to evaluation of sums instead of means of symptom scores, may be performed for the total symptom score, 6 domain symptom scores, and 3 component symptom scores.

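### The SAP has no rule for FluPRO AUC when a diary ends before Day 10; computed on the available entries, the AUC covers unequal windows and is too low for subjects who stop while symptomatic

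*SAP*

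**What the plan says.** SAP 9.1.1 sets the diary schedule: "The FluPRO data is collected at Day 1: Baseline, then every day through Day 10". For the total score, the six domain scores and the three component scores, the AUC "will be calculated using the linear trapezoidal rule", and on the window the SAP adds only "All time points from pre-dose to Day 10 will be considered".

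On missing data, SAP 4.2 says "Missing data will generally be left as missing, except for partial and missing AE and concomitant medication dates", and that special cases "will be described in the sections that describe the specific parameter's analysis". Section 9.1.1 has no such rule for the AUC. Its minimum-data rule works on items within one day ("Total symptom scores will only be calculated if the conditions of missing data for all domains are met"); it sets no minimum number of days.

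Other endpoints do have a rule. For FluPRO duration, "A missing value cannot contribute to the 2 consecutive" symptom-free days, and a subject who has not reached two consecutive symptom-free results by Day 10 is listed as more than 10 "and summarized as 10 days". For viral load, SAP 11.2 plans the analysis both without imputation and with the last observation carried forward. The one FluPRO sensitivity analysis in SAP 9.1.1 leaves out subjects who took antivirals in the first 10 days; it does not deal with missing diary days.

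**The concern.** An area under a curve can be compared between subjects only if it covers the same time. Two programmers following this text could produce different results, and each has a problem.

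- **Trapezoids on the available entries.** The area ends at the last entry. A diary that stops early gives a smaller area, which reads as milder illness.
- **AUC set to missing when Day 10 is absent.** The summary then describes only subjects who completed the diary.

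On the first reading the FluPRO summaries also conflict. A subject who stops on Day 4 without two consecutive scores at or below 1.0 receives the worst duration, 10 days, and at the same time a favourably low AUC.

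At stake is the interpretation of Tables 14.2.1.7A/B and 14.2.1.8A/B, which bear on the secondary objectives of symptom alleviation and severity. If stopping differs by arm, the AUC could show a difference that is not there or hide one that is.

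**Working it through.** The documents state no AUC value, completion rate or SD, so there is no figure to reproduce. The check applies the SAP's own formula to assumed symptom courses.

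**Inputs**
- Formula (SAP 9.1.1): each interval contributes ½ × (S_i + S_{i+1}) × (t_{i+1} − t_i).
- Schedule (SAP 9.1.1): daily to Day 10. Counting the baseline entry as Day 1 gives 10 entries and 9 one-day intervals.
- Item scores (SAP 16.3): 0 to 4, so no interval can contribute a negative area and a truncated AUC can never exceed the full one.
- Assumed course: mean total score falls in a straight line from 2.0 on Day 1 to 0.4 on Day 10, a slope of −1.6/9 = −0.178 per day.

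**One subject.** Full AUC = 9 × (2.0 + 0.4)/2 = 10.8. For a last entry on Day L, the score there is 2.0 − 0.178 × (L − 1), and AUC = (L − 1) × (2.0 + score)/2.

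| Last entry | Score that day | AUC on available entries | Change from 10.8 |
|---|---|---|---|
| Day 8 | 0.756 | 7 × 2.756/2 = 9.64 | −10.7% |
| Day 7 | 0.933 | 6 × 2.933/2 = 8.80 | −18.5% |
| Day 6 | 1.111 | 5 × 3.111/2 = 7.78 | −28.0% |
| Day 4 | 1.467 | 3 × 3.467/2 = 5.20 | −51.9% |

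On this course the score first falls to 1.0 or below on Day 7. A diary ending on Day 7 or earlier therefore has no two consecutive scores at or below 1.0, and the total-score duration is set to 10 days. A diary ending on Day 8 does have two.

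**Other assumed courses, diary ending on Day 4**
- Constant score of 2: 6.0 of 18.0, so 33% of the full AUC is kept.
- Linear 3 to 0.75: 7.88 of 16.88, 47% kept.
- Exponential from 2.5 with a 3-day half-life: 5.43 of 9.51, 57% kept.

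Order can reverse: the linear-course subject who stops on Day 4 (7.88) ranks below a subject with the milder exponential course who completes the diary (9.51).

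**Where nothing is lost**
- A gap inside the diary is bridged by the time difference in the formula. With Days 5 and 6 missing, the AUC is 16.88 against 16.88 (linear 3 to 0.75) and 9.61 against 9.51 (exponential). A day without a total score because one domain fails its minimum is bridged in the same way, unless it falls at either end of the diary.
- Once the score has reached 0, stopping costs nothing.

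**Arm mean.** With identical illness in both arms, the shift is the difference in stopping proportion times the loss per stopper. On the 2.0 to 0.4 course, 10% of one arm against 0% of the other gives:
- Day 8: 0.10 × 10.7% = 1.1%
- Day 7: 0.10 × 18.5% = 1.9%
- Day 4: 0.10 × 51.9% = 5.2%

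Equal stopping at the same day gives no shift between arms.

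**Simple repairs.** For the linear 3 to 0.75 course stopped on Day 4 (true AUC 16.88), carrying the last score forward gives 7.88 + 6 × 2.25 = 21.38. Scaling the time-average to 9 days gives 7.88/3 × 9 = 23.62. Both overstate the burden when symptoms are falling.

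**The case against.** The strongest reply is that the SAP nowhere says the AUC is summed only over completed diary days. That is an inference from silence, and leaving data missing also permits a missing AUC. This stands: the defect is an absent rule, not a wrong rule that was chosen. It does not remove the problem, because neither available reading gives a common window for all subjects.

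A reader might also infer that the sickest subjects will get the lowest AUC. The documents do not support that. Nothing in them says that worsening or hospitalised subjects stop the diary, and the population has uncomplicated influenza.

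Early stopping is also made less likely by near-daily contact: calls on about Days 2, 4 and 6, and clinic visits on Days 3, 5 and 7 at which the diary is checked. Ten percent against none at Day 4 is therefore an extreme case. After Day 7 that contact ends while the diary runs to Day 10, so a last entry on Day 7 or 8 is the more plausible case, with an effect of about 1% to 2% at the same differential.

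Finally, AUC is a descriptive summary. The FluPRO endpoint in SAP 3.2 is incidence, severity and duration; no test is named for FluPRO AUC; SAP 2.3 plans no formal testing; and Protocol 1.1 says the sample size does not support an efficacy determination. Daily scores are tabulated with n by arm, and Listing 16.2.6.1.4 shows compliance, so unequal loss would be partly visible. All of this limits the importance, but a descriptive summary should still measure every subject over the same time.

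**Conclusion.** The concern holds as an omission with a known direction. SAP 9.1.1 and 4.2 together leave FluPRO AUC undefined for a diary that ends before Day 10. On available entries, a subject who stops with symptoms remaining gets an AUC that can only be too low, by 11% to 52% for a last entry between Day 8 and Day 4 on the assumed course. If the subject has not had two consecutive scores at or below 1.0, the duration rule sets the same person to 10 days. If the AUC is set to missing instead, the summary is confined to completers.

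The percentages rest on an assumed course, and the arm-level effect rests on differential stopping, for which the documents give no rate. It would be tempting to conclude that the planned AUC will create a false treatment effect. That does not follow: equal stopping produces no bias between arms, and the more plausible late stopping produces a small one. The point is worth correcting because the summary is planned for ten scores and the correction uses data already collected.

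**What to change.** Before unblinding, amend SAP 9.1.1 as follows.

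1. Define FluPRO AUC over a common Day 1 to Day 10 window for every mITT subject.
2. Estimate the treatment comparison from a repeated-measures model of the daily scores, with baseline as covariate, and take the trapezoid-weighted contrast. With daily entries the weights are ½ for Day 1, 1 for each of Days 2 to 9 and ½ for Day 10, which sum to 9. Do this at least for the total score.
3. Keep the AUC from observed entries as a supportive summary, and state how it is derived for an incomplete diary.
4. Tabulate diary completion by day and arm.

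Do not make an AUC restricted to subjects with a Day 10 entry the main check, since that selects on something that happens after randomisation. Carrying the last score forward or scaling the time-average is not a safe substitute, for the reason shown in the working.

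The cost is some SAP wording, one table and a small amount of modelling; extending the model to all ten scores, by mean and by sum, would cost more. The model assumes that data are missing at random given the recorded scores. The SAP should state this assumption, because unrecorded worsening after the last entry would violate it.

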9.1.2 Patient Diary – Oral Temperature

Subjects are instructed to record an oral temperature every morning and evening, starting on Day 1 and continuing through Day 10. This data will be summarized, in degrees Celsius, at each visit/time point with continuous statistics n, mean, SD, median, minimum, and maximum. These summaries will be presented by treatment group, including the combined low-dose and high-dose VIS410 group. This summary will be performed using the mITT population. Time to recovery to normal temperature will be assessed for each treatment arm and the combined low-dose and high-dose VIS410 group. Normal temperature will be defined as 2 consecutive oral temperature of $<37.2^{\circ}\text{C}$ (99°F). Kaplan-Meier methods will be used to calculate the median time, 25th percentile, and 75th percentile time to normal temperature. This analysis will only include mITT subjects with a baseline temperature of $>38^{\circ}\text{C}$.

9.1.3 Complications of Influenza

The number and percentage of subjects in the mITT population with at least 1 complication of influenza will be summarized with counts, percentages, and the exact 95% CI of subjects with complications. A similar summary will be presented for each of the main complications of influenza: pneumonia, myocarditis, worsening of chronic bronchitis, otitis, sinusitis, death, other chronic pulmonary diseases, and other complications. These summaries will be presented for each treatment group as well as the combined low-dose and high-dose VIS410 groups.

9.1.4 Hospitalizations

Hospitalization parameters will be summarized for each treatment group and the combined low-dose and high-dose VIS410 groups, and overall subjects in the mITT population. The number and percentage of subjects hospitalized, and hospitalized for influenza-related complications, will be summarized with counts and percentages. The duration of hospitalization in days will be summarized with n, mean, SD, median, minimum, and maximum in the mITT population.

9.1.5 Influenza A Relapse

The incidence of relapse/reinfection will be summarized with counts and percentages in the mITT population for all 3 treatment groups and the combined VIS410 low-dose and high-dose groups as well as overall.

The initial screening for possible relapse will be based on MedDRA coded AE preferred terms of Flu-like symptoms, Flu-like aching, Flu-like illness, or Influenza-like symptoms. The start date

for this AE must be during the 100-day follow-up period and ≥ 7 days after any earlier influenza AE to ensure this is a relapse, rather than a worsening of initial symptoms. Relapses must be confirmed with a positive virology test.

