3.2 Secondary Endpoints

- The incidence, severity, and duration of signs and symptoms of influenza-like illness as assessed by the FluPRO questionnaire after a single IV dose of VIS410
- Percentage of participants requiring hospitalization for influenza-related complications
- Duration of hospitalization for influenza-related complications
- Percentage of participants with complications of influenza
- Percentage of participants with influenza A relapse/reinfection
- VIS410 PK parameters (C_{max} , t_{max} , $AUC_{0-\infty}$, AUC_{0-last} , $t_{1/2}$, V_d , CL) in serum
- The difference between VIS410 and placebo treatment groups in viral AUC from nasopharyngeal swabs
- The difference between VIS410 and placebo treatment groups in peak viral load and time to resolution of viral load from nasopharyngeal swabs

- Titer of anti-VIS410 antibody-positive samples

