5.1.2 Modified Intent-to-Treat Population

The mITT population will include all subjects who receive IV study drug and are confirmed influenza A positive by a molecular test at the central virological laboratory.

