5.1.4 Pharmacokinetic Population

The PK population will include all subjects who receive IV study drug and have at least 1 PK parameter that can be calculated. Nasopharyngeal swabs that are collected outside of the protocol defined sampling time points for PK (i.e. when influenza-like symptoms are present) will not be used to determine PK parameters. Nasopharyngeal PK parameters will only be calculated for the first 50 subjects enrolled.

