16 APPENDICIES

16.1 Changes to the Protocol Specified analyses

ADA data at Day 14 will not be analyzed.

Nasopharyngeal viral load samples will only be analyzed for qPCR and TCID₅₀ until Day 7, unless still positive on Day 7, and then samples will also be analyzed on Day 14. No PCR or TCID₅₀ samples are planned to be analyzed post-Day 14.

QTcF interval prolongation categories were updated to <450, >450 to ≤480, >480 to ≤500, and >500 msec and categories for QTcF increases were updated to <30, >30 to ≤60 and >60 msec from Baseline.

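### Relapse needs virology confirmation over 100 days (SAP 9.1.5), but SAP 16.1 plans no assay after Day 14, and the AE screen and 7-day gap can miscount episodes

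*SAP*

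**What the plan says.** SAP 3.2 lists "Percentage of participants with influenza A relapse/reinfection" as a secondary endpoint. SAP 9.1.5 summarises it with counts and percentages in the mITT population, that is "all subjects who receive IV study drug and are confirmed influenza A positive by a molecular test". An episode counts if it passes three rules:

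- **Screen.** The first look is at "MedDRA coded AE preferred terms of Flu-like symptoms, Flu-like aching, Flu-like illness, or Influenza-like symptoms".
- **Gap.** The AE must start within the 100-day follow-up and at least "7 days after any earlier influenza AE to ensure this is a relapse, rather than a worsening of initial symptoms".
- **Confirmation.** "Relapses must be confirmed with a positive virology test". No assay, laboratory or swab is named.

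On laboratory work, SAP 16.1 analyses viral load samples by qPCR and TCID50 to Day 7, "unless still positive on Day 7, and then samples will also be analyzed on Day 14". It adds that no PCR or TCID50 "samples are planned to be analyzed post-Day 14". SAP 11.2 lists viral load for the first 50 subjects through Day 14 and attaches no Day 7 condition.

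On swabs, protocol Table 1 schedules those from Day 14 onward for the first 50 subjects only (footnote 21). Footnote 22 asks for extra swabs when influenza-like illness is reported.

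**The concern.** The endpoint definition depends on a test result, while another part of the same SAP stops the testing well before follow-up ends. If the illness swabs fall under that stop, a subject with a true late relapse could be swabbed as the protocol asks and still have no result that lets the episode count. A zero in the table would then read as no relapses when it may mean no test.

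The screen and the gap add errors of their own, in opposite directions. A screen that leaves out the plain diagnosis can lose true episodes. A gap with nothing to measure from can let in a worsening of the first illness. What is at stake is which episodes are counted for a named secondary endpoint.

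**Working it through.** There is no planned figure to reproduce. Neither document gives an expected relapse rate or a sample size calculation for this endpoint. The check sets the rules side by side and follows illustrative subjects through them.

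**1. Confirmation.**
- SAP 9.1.5 allows onset at any time in the 100 days. SAP 16.1 ends PCR and TCID50 at Day 14 and states no exception.
- The SAP does recognise illness swabs. Section 5.1.4 says that "Nasopharyngeal swabs that are collected outside of the protocol defined sampling time points for PK (i.e. when influenza-like symptoms are present") are not used for PK parameters. Sections 9.1.5, 11.2 and 16.1 give no matching rule for virology.
- For subjects outside the first 50, illness swabs are the only study swabs the schedule provides after Day 7.
- Footnote 22 says these swabs should be taken. Protocol 7.1.6 leaves swabbing at an unscheduled visit to the Investigator.

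*Subject A (illustrative):* virus-negative on Day 7, new illness on Day 40, recorded under one of the four listed terms, swabbed under footnote 22. The screen and gap are passed. On a literal reading of 16.1 no confirming assay is planned, so the episode does not count unless a local test exists and is accepted.

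**2. Day 14.** For a first-50 subject who is negative on Day 7, 16.1 gives no Day 14 assay, whereas 11.2 expects viral load to be listed through Day 14. The two sections disagree.

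**3. Screen.** Protocol 10.6 prefers a diagnosis to a list of symptoms. A site following it may record a new episode as influenza, which is not among the four terms.

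*Subject B (illustrative):* as A, but the AE is recorded and coded as influenza. The episode fails the screen whatever the swab shows.

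Recording rules add to this. Protocol 7.3.2, 9.3.8 and 10.1 each restrict AE reporting of influenza symptoms, with three different exceptions (Investigator opinion, relationship to study medication, and resulting in an SAE) and no end date. A site could read them as applying to a new episode weeks later.

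**4. Gap.** Under protocol 7.3.2 and 10.1 the enrolment illness is normally not an AE. Without an earlier influenza AE there is nothing from which to count 7 days, and the condition is met by default.

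*Subject C (illustrative):* a worsening on Day 4 is recorded as a first flu-like AE, and the Day 5 swab is still positive. It passes the screen, meets the gap by default and has a positive test, so it counts as relapse, although the gap rule exists to exclude it. If the gap ran from the Day 1 infusion, to take one possible date, the earliest countable onset would be Day 1 + 7 = Day 8, and C would be excluded.

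**The case against.** The strongest reply is that 16.1 concerns scheduled viral load samples. It speaks of viral load samples and limits them by visit day, and illness swabs are unscheduled. Protocol 7.1.5 sends swabs collected under the schedule to a central virology laboratory, and footnote 22 is part of that schedule. By demanding confirmation, 9.1.5 presupposes that somebody tests them. Local tests are also permitted, and the laboratory manual and analytical plan are not available here. This may well be the intent, and it rules out saying that a late relapse cannot be confirmed. It does not remove the problem: the closing sentence of 16.1 is general, no exemption is written, and 9.1.5 does not say whether a local result counts.

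It is also fair that 9.1.5 calls the AE terms an initial screen, that the symptom restrictions name individual symptoms and do not clearly bar a new illness, and that subject C requires several things to coincide. No frequency is available for any of these.

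Two stronger readings are tempting. A reader might treat the share of follow-up without a planned assay as a measure of missed relapses. It is not, because relapse is found from a symptom AE and then confirmed, not through surveillance swabs. A reader might also infer that testing differs by arm, since under 16.1 the Day 14 assay depends on the Day 7 result. The documents do not support that for relapse, for the same reason, and because 11.2 lists Day 14 data for the first 50 with no such condition.

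Finally, the endpoint is descriptive, with no test and no confidence interval planned, in a Phase 2a safety study. That limits the weight of the point but does not make the rules consistent.

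**Conclusion.** The concern holds as a problem of definition. Read literally, 16.1 leaves a late relapse without a planned confirming assay, and it conflicts with 11.2 on Day 14 for subjects negative on Day 7. The screen in 9.1.5 misses an episode coded as influenza. The gap rule can be met by default.

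The first and third of these can lower the count, and the last can raise it, so the net direction is unknown. The number of episodes affected cannot be computed from the documents. The conclusion rests on the literal text of 16.1 and on sites following protocol 7.3.2, 10.1 and 10.6 as written. It should be corrected before unblinding, but it does not touch the primary safety objective.

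**What to change.** 1. **SAP 16.1:** exempt illness-triggered swabs from the cut-off and assay them by qRT-PCR for influenza A through Day 100. Otherwise, report relapse after the last planned test as not evaluated, not as 0%.
2. **SAP 9.1.5, screen and test:** add AEs coded as influenza, name the confirming test, and say whether local results count.
3. **SAP 9.1.5, gap:** treat the enrolment illness as the earlier episode. Measure the gap from a prespecified date that every mITT subject has, and require the confirming swab at or after onset of the new episode. The documents do not dictate which date; the infusion date is one candidate, though a prolonged first illness could still pass a gap counted from it.
4. **Reporting:** show suspected, tested and confirmed episodes by arm beside the percentage.
5. **Reconcile:** protocol 7.3.2, 9.3.8 and 10.1 on recording a new influenza-like illness; footnote 22 with protocol 7.1.6; SAP 11.2 with 16.1 on Day 14 assays.

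The cost is SAP and protocol wording plus a few extra assays on swabs the protocol already calls for. If the later period is reported as not evaluated, no illness-swab assays are added.
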